8.3.9 Event of Special Interest

There are no events of special interest related to Albutein 20%.

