In addition, long-term human albumin administration may also modulate the deleterious effects of inflammatory mediators on mitochondrial and cell function and on organ microcirculation, thus protecting target organs against tissue damage and microcirculatory disturbances. These effects could potentially reduce the incidence of decompensation episodes (ie, ascites, renal or liver failure, hepatic encephalopathy (HE), severe sepsis, septic shock, and acute-on-chronic liver failure [ACLF]) and increase survival rates (21).

Albutein is made from pooled human plasma. Based on effective donor screening and product manufacturing processes, it carries an extremely remote risk for transmission of viral diseases, including a theoretical risk for transmission of Creutzfeldt-Jakob disease (CJD). Although no cases of transmission of viral diseases or CJD have ever been identified for albumin, the risk of infectious agents cannot be totally eliminated (1).

Albutein is contraindicated in patients with severe anemia or cardiac failure in the presence of normal or increased intravascular volume. The use of Albutein is contraindicated in patients with a history of allergic reactions to this product. The most serious adverse reactions (ARs) are anaphylactic shock, heart failure, and pulmonary edema. The most common ARs are anaphylactoid type reactions. For additional information on potential risks and adverse events (AEs), please also refer to the IB (1) and any additional data supplied by the sponsor.

2.4 Description of and Justification for the Route of Administration, Dosage, Dosage Regimen, and Treatment Periods

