5.3.2 Discontinuation of Subjects from Treatment

If a subject receives a liver transplant, study treatment and all treatment-related assessments will be discontinued upon transplant. The criteria to determine when a subject becomes a candidate for liver transplantation is described in Section 5.3.2.1. The subject will continue to have subsequent planned visit assessment procedures performed.

Discontinuation of the treatment in subjects who receive a TIPS insertion will be at the discretion of the investigators. In case it is decided to discontinue the subject's treatment early, study treatment will be stopped and the subject will continue to have subsequent planned visit assessment procedures performed.

Adverse events that will determine temporary subject's discontinuation from study treatment include the following:

• Subjects developing severe bleeding, Albutein 20% infusions will be temporarily stopped until the bleeding episode is resolved. For subjects with variceal bleeding, Albutein 20% infusions will be temporarily stopped until the subject has received at least 2 banding sessions. Albutein 20% infusions will be resumed after the bleeding episode is resolved or after the subject has received at least 2 banding sessions, respectively.

Adverse events that will determine permanent subject's discontinuation from study treatment include the following:

- Anaphylactic shock or transfusion-related acute lung injury
- Severe AEs (ie, acute myocardial infarction, cerebral hemorrhage, cardiac failure, pulmonary edema, or intestinal necrosis) that precludes the continuation of the subject in the clinical study

Subjects with any one of these severe AEs will be discontinued from study treatment and all treatment-related assessments, and should continue to have subsequent planned visit assessment procedures performed.

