6.2.4 Cardiac Overload/Pulmonary Edema Treatment

In subjects with the diagnosis of cardiac overload/pulmonary edema, standard protocols will be applied as per institution standards and may include fluid restriction, IV administration of furosemide, and Renal Replacement Therapy if clinically indicated (diuresis lower than 0.5 mL/kg under high doses of furosemide). See Appendix 9 for an example of Algorithm for Cardiogenic Pulmonary Overload and Appendix 10 for guidelines on the management of pulmonary edema.

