9.1.3 Safety Analysis

The safety analyses will be addressed by listing and tabulation of AEs (including suspected ADRs), vital signs, physical assessments, and clinical laboratory tests. Data will be described using descriptive analyses and treatment comparisons will be based on review of descriptive statistics. The safety analyses will be based on the Safety population.

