5.4.2 Safety Variables

The following safety variables will be assessed in this study:

- The number of suspected adverse drug reactions (ADRs; defined as possibly and or definitely drug related), including ARs (defined as definitely drug related), and incidence rate of subjects with suspected ADRs during the treatment period and within 72 hours after Albutein 20% infusion completion (or after Albutein 20% infusion stops) will be considered as the main safety variables. Due to the open label design of this trial, ADRs will be assigned causality to Albutein and ADRs will not be applicable to SMT.
- The number and incidence rate of overall treatment-emergent adverse events (TEAEs) and Serious AEs (SAEs), in addition deaths and discontinuations due to AEs will be also collected and analyzed.
- Clinically significant/relevant changes in vital function and clinical laboratory testing parameters, as determined by the investigator, will be documented as AEs and reported as part of the adverse event summaries.
- Vital signs (temperature, blood pressure, heart rate, respiratory rate) at each scheduled visit and, in particular before and after each Albutein 20% administration.
- Clinical laboratory test parameters including:
- Chemistry (Sodium, potassium, creatinine, blood urea nitrogen (BUN), calcium, magnesium, lactate dehydrogenase (LDH), aspartate aminotransferase (AST), alanine aminotransferase (ALT), gamma-glutamyl transpeptidase (GGT), alkaline phosphatase (ALP), glucose, total bilirubin, direct and indirect bilirubin, C-reactive protein (CRP), serum albumin [pre and post albumin 20% infusion in the SMT + A20% group])
- Hematology (Hemoglobin, hematocrit, platelets, red blood cell count, white blood cell (WBC) count with differential, total neutrophils, lymphocytes, monocytes, eosinophils, basophils)
- Lactate
- Coagulation (International normalized ratio (INR), fibrinogen, prothrombin time)
- Albumin functional capacity assessment (Albumin binding capacity)
- Urine pregnancy test (Qualitative urine β -human chorionic gonadotropin [β -HCG])
- Procalcitonin
- Biomarker (interleukin [IL] 6 (IL-6), IL-8, IL-10) and tumor necrosis factor alpha [$TNF\alpha$])

Number	BIG-CL-SP-000319		
	IG1601	Statistical Analysis Plan	
Effective Date	09-Sep-2024	Status	2.0
Effective	19 of 52		
Page			

- Plasma biomarker retains and transcriptome
- Physical examinations

6 General Statistical Considerations

All analyses will be conducted using SAS Version 9.4 or higher.

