10.1 Adverse Events

Adverse Events are coded using the MedDRA coding dictionary (a version within 1 year of the data base lock). A treatment emergent adverse event (TEAE) is defined in [Section 6.1.6](#). A suspected ADR is an adverse event with causal relationship of "definitely related" or "possibly related", as classified by the investigator. An adverse reaction (AR) is an adverse event with causal relationship of "definitely related", as classified by the investigator.

A temporally associated (i.e., infusional) AE is an AE that is temporally associated with the infusion of Albutein 20%, and is identified as an AE that occurs during an Albutein infusion (as recorded by the investigator), or within 72 hours following an Albutein infusion (determined by calculating the time from infusion end to AE start). These definitions only apply to subjects in the SMT + Albutein 20% group.

All adverse events, both treatment-emergent and non-treatment emergent, will be included in a listing, with a flag to distinguish whether or not the event is treatment-emergent.

An overall summary of TEAEs will present the number of TEAEs, and the number and percentage of subjects with TEAEs, in the following categories:

- AE with Onset Prior to Treatment
- TEAE
- Suspected ADR
- AR
- TEAE Leading to Death
- Serious TEAE
- Serious Suspected ADR
- Serious AR
- Non-Serious TEAE
- TEAE Leading to Drug Interruption
- TEAE Leading to Drug Withdrawal
- TEAE Leading to Study Withdrawal

GRIFOLS	Number	IG1601	Big-CL-SP-000319
	Version	2.0	Statistical Analysis Plan
	Effective	Effective Date	09-Sep-2024
	Page		41 of 52

- Temporally associated TEAEs

In addition, TEAEs will be summarized in the following ways:

- SOC / PT – summary of number of TEAEs and number/percentage of subjects with at least one TEAE by treatment, SOC and preferred term
 - A select subset of TEAE summaries will also include number of events by SOC and preferred term
- PT – summary of number of TEAEs and number/percentage of subjects with at least one TEAE by treatment and preferred term
- SOC/PT/Severity – summary of number of TEAEs and number/percentage of subjects with at least one TEAE by treatment, SOC, preferred term, and severity
- SOC / PT / Causality – summary of number of TEAEs and number/percentage of subjects with at least one TEAE by treatment, SOC, preferred term, and causality

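### Cardiac failure and pulmonary edema are a main named hazard of Albutein, but no planned table counts overload events as one group in both arms, so a modest between-arm difference could be diluted

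*Protocol*

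**What the plan says.** **Hazard.** Protocol 2.3 states: "The most serious adverse reactions (ARs) are anaphylactic shock, heart failure, and pulmonary edema". It also contraindicates the product in cardiac failure with normal or increased intravascular volume. Section 5.3.2 lists severe events that end study treatment permanently when they preclude continuation: "acute myocardial infarction, cerebral hemorrhage, cardiac failure, pulmonary edema, or intestinal necrosis". Section 6.2.4 begins: "In subjects with the diagnosis of cardiac overload/pulmonary edema, standard protocols will be applied as per institution standards", and it refers to Appendices 9 and 10. Exclusion criterion 10v4 keeps out subjects with heart failure.

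**Designation.** Protocol 8.3.9 consists of one sentence: "There are no events of special interest related to Albutein 20".

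**Analysis.** Protocol 9.1.3 says that "treatment comparisons will be based on review of descriptive statistics". The core table in SAP 10.1 is a "summary of number of TEAEs and number/percentage of subjects with at least one TEAE by treatment, SOC and preferred term". SAP 10.1 adds breakdowns by severity and causality, subsets for serious events, study withdrawal and death, rates per infusion and per exposure week, and a by-subject listing. It contains no grouped overload category.

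**What covers one arm only.** Protocol 8.1 makes suspected adverse drug reactions, including those within 72 hours of an infusion, the main safety variables. SAP 5.4.2 says "ADRs will be assigned causality to Albutein and ADRs will not be applicable to SMT". SAP 10.1 restricts temporally associated events to the Albutein group, and the preferred-term rates per infusion likewise.

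**The concern.** The sponsor has identified a specific hazard of repeated albumin infusion, but the plan attaches no analysis to it. Exposure is substantial: up to 37 infusions (SAP 8.4) of up to 100 g each (Protocol 6.1.1).

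Overload can be recorded under more than one diagnosis. The protocol itself uses heart failure, cardiac failure, pulmonary edema and cardiac overload. A subject recorded under one term and a subject recorded under another fall in different rows. Control subjects can also receive albumin, after paracentesis or for certain complications (Protocol 4.4.1.2), so the question is one of excess over SMT and needs the same count in both arms.

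The outputs tied most closely to the infusion cannot supply that count, because they have no control-arm counterpart. What remains for comparing arms is a set of separate rows, each with few subjects, plus listings. A modest real difference could look unremarkable row by row.

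**Working it through.** **1. Which planned outputs could give a by-arm overload count?**

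| Output (SAP) | Both arms? | Pools overload terms? |
|---|---|---|
| Suspected adverse drug reactions (5.4.2, 10.1) | No | No |
| Temporally associated events, 72 h (10.1) | No | No |
| Preferred-term rates per infusion or exposure week (10.1) | No | No |
| TEAE leading to drug withdrawal, one overall line (10.1) | No Albutein to withdraw under SMT | Mixes all causes |
| SOC/PT tables, with severity and causality (10.1) | Yes | No |
| Serious, fatal and study-withdrawal subsets by SOC/PT (10.1) | Yes | No |
| By-subject listing (10.1) | Yes | Only by later hand count |

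The subset table in SAP 10.1 gives SOC/PT detail for study withdrawal but not for drug withdrawal. An SOC total mixes overload with unrelated events and is not an overload category.

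**2. Denominator.** Protocol 9.2 gives 205 per arm, from 46% versus 31%, two-sided 5%, 80% power and 20% dropout. With n = [1.96·√(2·0.385·0.615) + 0.8416·√(0.46·0.54 + 0.31·0.69)]² / 0.15², the result is 164.01, rounded up to 165 per arm or 330 in total. Then 330/0.8 = 413, against 410 stated. The 164 evaluable per arm (205 × 0.8) give power 0.800. The figure reproduces and is used here only as the safety denominator.

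**3. Illustration of dilution.** The documents give no overload rate, so the rates are assumed. The method is the exact probability that a two-sided Fisher test at 205 per arm gives p ≤ 0.05 with the excess on Albutein. This is computed for the pooled count and for one row carrying a third of the events. Treating rows as independent, the chance for any of three rows is 1 − (1 − given row)³.

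| Assumed rate, Albutein vs SMT | Expected pooled subjects | Pooled | Given row of three | Any row of three |
|---|---|---|---|---|
| 10% vs 3% | 20.5 vs 6.2 | 79% | 24% | 56% |
| 8% vs 2% | 16.4 vs 4.1 | 76% | 20% | 48% |
| 6% vs 2% | 12.3 vs 4.1 | 45% | 8% | 22% |
| 4% vs 1% | 8.2 vs 2.1 | 37% | 3% | 9% |

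For the first line, 1 − (1 − 0.237)³ = 0.556. With only two equal terms, 10% versus 3% gives 41% for a given row and 1 − (1 − 0.41)² = 65% for either.

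**4. The same dilution as an estimate.** Take 20 versus 6 pooled subjects. The risk difference is 20/205 − 6/205 = 6.8 points, with standard error √(0.0976·0.9024/205 + 0.0293·0.9707/205) = 2.38 points. The 95% CI is 2.2 to 11.5. One of three rows would hold about 7 versus 2 subjects. The difference is 2.4 points, the standard error is √(0.0341·0.9659/205 + 0.0098·0.9902/205) = 1.44 points, and the 95% CI is −0.4 to 5.3.

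**The case against.** **Section 8.3.9 is a reporting designation.** It sits among the procedures for recording and reporting adverse events. Declining that label does not deny the risks in 2.3, and serious adverse events already go to the sponsor within 24 hours. This stands: a reader might infer a flat contradiction, but the text supports only a mismatch between hazard and designation. The practical gap is in SAP 10.1.

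**The planned views go beyond SOC and PT, and the count is recoverable.** A reader might infer that events are tabulated only by organ class and term, or that the number of affected subjects could never be recovered. Neither is so. SAP 10.1 plans several other views and a full listing, from which unique subjects can be counted, and SAP section 2 allows further analyses documented in the study report. But a grouping chosen after by-arm data have been seen in an open-label trial carries less weight than one fixed beforehand.

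**Scatter is assumed.** Protocol 8.3.8 asks that related signs be recorded as one diagnosis where possible. That limits splitting within a subject's event. It does not pool subjects given different diagnoses. If one term carried 70% of events, that row alone would reach 60% at 10% versus 3%.

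**Single-row power overstates the loss.** A reviewer scans all rows and would notice a consistent direction. Even with five equal terms, at least four rows lean towards Albutein in about 85% of trials at 10% versus 3%, and 82% at 8% versus 2%. This is why the any-row figures are given. They still fall short of the pooled ones.

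**The DSMB may look at overload.** Its charter is not among the documents, so this can be neither credited nor excluded.

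**Conclusion.** The concern holds as a gap in the planned safety summaries. The protocol names the hazard, and no planned output gives one overload count by arm. The main safety variables cannot fill the gap because they exist only for Albutein.

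Under the assumed 10% versus 3%, the chance of a nominal difference falls from about 79% pooled to 56% for any of three rows, or 24% for a given row. Under 8% versus 2% it falls from 76% to 48% or 20%. These figures rest on assumed rates, an even three-way split, independent rows and all 205 subjects per arm counted. They are not operating characteristics of the plan, which makes no formal safety test.

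A reader might infer that an overload signal will be missed. The documents support only that a modest difference could be diluted, since serious-event reporting, listings and the DSMB remain. Nor do they support saying that the safety objective turns on overload: it covers general safety and tolerability. The primary efficacy conclusion is unaffected.

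**What to change.** Add to SAP 10.1 one grouped category for cardiac failure, pulmonary edema and fluid overload, defined by a MedDRA preferred-term list fixed before any by-arm review or, at the latest, before database lock. On the Safety population, report by arm:

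- subjects with at least one event in the group, each counted once;
- serious events and fatal events in the group;
- the risk difference with its 95% CI, described as an estimate without a formal test.

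At the next protocol amendment, reconcile the wording of 8.3.9 with 2.3, 5.3.2 and 6.2.4. The SAP change does not have to wait for it, and no clinical management rule changes.

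The cost is agreement on the term list in advance and one extra table. The data are already collected.

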8.3.10 Disease Progression

In this clinical study, disease progression is defined as the worsening of a subject's condition attributable to the disease for which the IP is being studied. It may be an increase in the severity of the targeted disease and/or increases in the symptoms of the targeted disease. Anticipated disease progression includes, but not limited to: HE, GI bleeding, portal hypertension, ascites, SBP, hyponatremia and HRS.

The development of sequelae of decompensated cirrhosis during the clinical study should be considered as disease progression and not an AE, unless there is evidence suggesting a causal relationship between the study drug and the AE. Manifestations of decompensated cirrhosis will be treated as disease progression and will be documented in the eCRF and subject's medical records, but not immediately reported to the sponsor.

Hospitalization due to disease progression and/or the signs and symptoms of disease progression should not be reported as an SAE during the study.

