- 12v5. Subjects with nephropathy with renal failure with serum creatinine >2 mg/dL or systemic hypertension.
- 13v5. This criterion has been removed from protocol Version 5.
- 14. Subjects with severe psychiatric disorders.

- 15. Subjects with a known infection with human immunodeficiency virus (HIV) or have clinical signs and symptoms consistent with current HIV infection.
- 16. Females who are pregnant, breastfeeding, or if of childbearing potential, unwilling to practice effective methods of contraception (oral, injectable, or implanted hormonal methods of contraception, placement of an intrauterine device or intrauterine system, condom, or occlusive cap with spermicidal foam/gel/cream/suppository, male sterilization, or true abstinence*) throughout the study.
 - * True abstinence: When this is in line with the preferred and usual lifestyle of the subject (periodic abstinence [eg, calendar, ovulation, symptothermal, post-ovulation methods], declaration of abstinence for the duration of the clinical study, and withdrawal are not acceptable methods of contraception).
- 17. Subjects with previous liver transplantation.
- 18. Subjects with known or suspected hypersensitivity to albumin.
- 19. Subjects participating in another clinical study within 3 months prior to screening.
- 20v4. Subjects with active drug addiction (exceptions: active alcoholism or marijuana).
- 21. In the opinion of the investigator, the subject may have compliance problems with the protocol and the procedures of the protocol.
- 22. Subjects with ongoing or recent variceal bleeding (subjects can be included 2 weeks after hemorrhagic episode).
- 23. Subjects with septic shock at screening.
- 24. Subjects with ongoing SBP infection (subjects can be included upon resolution).
- 25. Subjects with current infection of COVID19, those who are less than 14 days post recovery, or those who have clinical signs and symptoms consistent with COVID19 infection.

Investigational Product, Dose and Mode of Administration

Albutein 20% is the investigational product (IP).

Following randomization, subjects will receive the first Albutein 20% infusion at the dose of 1.5 g/kg body weight (maximum 100 grams per subject). Thereafter, subjects will receive Albutein 20% infusions at the dose of 1.5 g/kg body weight (maximum 100 grams per subject) every 10 ± 2 days for the rest of the study (up to a maximum of 12 months). Subjects in this treatment group will also receive SMT.

Duration of Treatment:

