4.3.3 Blinding

Not applicable. This is an open-label study.

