8.3.3 Adverse Event Definitions

8.3.3.1 Adverse Events

An AE is defined as any untoward medical occurrence in a subject or clinical investigation subject administered a medicinal product or study treatment and which does not necessarily have a causal relationship with this administration. An AE can therefore be any unfavorable and unintended sign (including any abnormal laboratory finding, for example), symptom, or disease temporally associated with the use of a medicinal product, whether or not considered related to the medicinal product. This includes worsening of a pre-existing condition or increase in frequency of a pre-existing condition.

An AE is also defined as any occurrence that is new in onset, expected, or aggravated in severity or frequency from a baseline condition, or abnormal results or diagnostic procedures including laboratory test abnormalities.

In this clinical study, deterioration of the targeted disease and symptoms associated with the targeted disease will not be considered an AE as long as the deterioriation is anticipated and there is no evidence suggesting a causal relationship between the study drug and the AE. Anticipated disease progression includes, but not limited to: HE, GI bleeding, portal hypertension, ascites, SBP, hyponatremia and HRS (see Section 8.3.10).

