9.3.8 Incidence of Disease-Related Complications

GRIFOLS	Number	IG1601	Big-CL-SP-000319	Version	2.0	Status	Effective	Effective Date	09-Sep-2024	Page	38 of 52
	IG1601 Statistical Analysis Plan										

All disease-related complications will be collected via a eCRF through Month 12 and will be listed.

The number and percentage of subjects with at least one occurrence of each of the following disease-related complications from the list below on or after treatment start date will be presented by treatment, and compared using the generalized linear models implemented in SAS GENMOD procedure, in which the odds ratio and corresponding 95% Confidence Interval (CI) will be determined from a logistic model, with the incidence of disease related complication (Yes/No) as the dependent variable and treatment, stratification factors of region (Europe or North America) and history of hospitalization for acute decompensation of liver cirrhosis (yes or no) as factors. The robust variance estimate for the treatment effect will be estimated based on the compound symmetry working correlation structure. If the model does not converge, first-order autoregressive (AR (1)) working correlation structure will be used. If it fails to converge, the independent working correlation structure will be used.

Anticipated disease related complications will include:

- HE – including HE I, HE II, HE III, and HE IV
- GI Bleeding – including lower GI bleeding and upper GI bleeding
- Portal Hypertension
- Ascites
- Spontaneous Bacterial Peritonitis
- Hyponatremia
- HRS – including Type 1 and Type 2
- Other (includes disease related complications not captured in the types listed above)

In addition, the number of each type of disease-related complications will be counted for each subject and presented by treatment as a continuous variable and as a categorical variable with categories 0, 1, 2, 3, 4 or more. No analysis of treatment differences will be performed.

9.3.9 Serum Albumin Concentration and Albumin Functional Capacity in Serum (Albumin Binding Capacity)

Serum albumin concentration and albumin binding capacity are analyzed by a central laboratory, with all results and normal ranges reported in SI units. Serum albumin concentration is measured before and after each infusion at each visit during the treatment period; albumin binding capacity is measured once per visit.

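### Cirrhosis complications can become adverse events through drug attribution in the Albutein arm only, so the between-arm AE tables are uneven; the plan also leaves open whether attributed events still count as complications

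*Protocol*

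**What the plan says.** **Classification rule.** Protocol 8.3.3.1 says that deterioration of the target disease "will not be considered an AE as long as the deterioriation is anticipated and there is no evidence suggesting a causal relationship" with study drug. Protocol 8.3.10 repeats the rule for sequelae of decompensated cirrhosis, which "should be considered as disease progression and not an AE, unless there is evidence suggesting a causal relationship" with study drug. The anticipated events named are HE, GI bleeding, portal hypertension, ascites, SBP, hyponatremia and HRS. The same section defines progression as worsening attributable to the disease under study, and says that manifestations of decompensated cirrhosis are documented in the eCRF.

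**Who can attribute, and in which arm.** The synopsis names Albutein 20% as the investigational product; SMT is the reference therapy. Protocol 4.3.3 on blinding reads "Not applicable. This is an open-label study". SAP 5.4.2 states that "ADRs will be assigned causality to Albutein and ADRs will not be applicable to SMT".

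**What is compared.** SAP 10.1 tabulates TEAEs and serious TEAEs by treatment, and Protocol 9.1.3 bases the comparison on review of descriptive statistics. The exploratory complication endpoint refers to 8.3.10 (Protocol 7.1.3). SAP 9.3.8 says "All disease-related complications will be collected via a eCRF through Month 12 and will be listed", then compares the proportion of subjects with at least one occurrence of each type by a logistic model with an odds ratio and 95% CI.

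**A related wording conflict.** Protocol 5.3.2, under a lead-in that calls the events adverse events, says "Subjects developing severe bleeding, Albutein 20% infusions will be temporarily stopped until the bleeding episode is resolved". Protocol 8.3.10 lists GI bleeding as anticipated progression.

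**The concern.** For an anticipated complication, suspected drug causality is what turns the event into an AE. That route exists only where there is a study drug, and the person making the attribution knows the arm. The same HE episode or GI bleed can then appear in the TEAE table for an Albutein subject and not for an SMT subject, with no difference in what happened. Safety and tolerability is a stated objective, and these tables are how it is answered.

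A second question follows. If an attributed event is treated as an AE instead of progression, it may never reach the complication record. Events would then leave the complication count in one arm only, and the comparison in SAP 9.3.8 would favour Albutein.

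**Working it through.** The plan states no figure on this point, so there is nothing to reproduce. The check has two parts.

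**1. Reading the rules together, by arm**

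| Event | Albutein arm | SMT arm |
|---|---|---|
| Anticipated complication, no suspected drug cause | Progression, not an AE | Progression, not an AE |
| Anticipated complication, drug cause suspected | AE | Cannot arise |
| Unanticipated deterioration (8.3.3.1) | AE | AE |
| Laboratory abnormality worsening to a medically significant degree (8.2.3) | AE | AE |
| Death not unequivocally due to progression (8.3.11.2) | SAE | SAE |

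Only the second row differs by arm. That row is enough to make the TEAE comparison depend on arm for these events, and its direction is extra AEs under Albutein.

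Whether a second-row event also stays on the complication record is not settled:
- For leaving it off: 8.3.10 defines progression as worsening attributable to the disease; the endpoint points to 8.3.10; SAP 6.1.4 lists AE dates and disease-related complication dates as separate items; SAP 9.3.8 does not mention AEs.
- For keeping it on: the documentation sentence in 8.3.10 has no causality exception, and SAP 9.3.8 collects all complications and states no exclusion.

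**2. Size, if attributed events are left off**

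Inputs: n = 205 per arm (Protocol 9.2). Assumed, because the documents give neither: true incidence p, equal in both arms, and share a of affected Albutein subjects who drop out of the complication count.

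- Observed Albutein proportion: q = p(1 − a)
- Odds ratio: [q/(1 − q)] / [p/(1 − p)]
- Albutein subjects with a complication shown as an AE: 205 × p × a (SMT: 0)
- Rejection rate: two-sided 5% pooled two-proportion test, 205 per arm

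Worked case, p = 0.20 and a = 0.10: q = 0.18; odds ratio = (0.18/0.82)/(0.20/0.80) = 0.2195/0.25 = 0.88; 205 × 0.20 × 0.10 = 4.1 subjects.

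| p | a | q | Odds ratio | Rejects at 5% | Subjects moved |
|---|---|---|---|---|---|
| 0.20 | 0.10 | 0.18 | 0.88 | 8% | 4.1 |
| 0.20 | 0.20 | 0.16 | 0.76 | 18% | 8.2 |
| 0.40 | 0.10 | 0.36 | 0.84 | 13% | 8.2 |
| 0.40 | 0.20 | 0.32 | 0.71 | 39% | 16.4 |
| 0.60 | 0.10 | 0.54 | 0.78 | 23% | 12.3 |
| 0.60 | 0.20 | 0.48 | 0.62 | 69% | 24.6 |

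If attributed events are recorded in both places, q = p, the odds ratio is 1.00 in every row, and only the AE tables change.

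The share a is a share of subjects. SAP 9.3.8 counts subjects with at least one occurrence, so a subject leaves the count only if every event of that type is attributed. With recurrent events, a is smaller than the share of events attributed.

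**The case against.** A reader might infer that the complication comparison is biased by construction and that the Albutein arm necessarily loses events. The documents do not support that. The rule decides whether an event is an AE; no sentence removes it from the complication page, and the text in 8.3.10 and SAP 9.3.8 can be read as requiring it there. eCRF completion instructions, which are not part of these documents, may settle the matter. This part of the objection stands, so the complication half is an ambiguity with a one-sided consequence.

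A reader might also infer that no control-arm cirrhosis event can reach the AE tables. That is too strong: the last three rows of the first table are open in both arms, and hyponatremia, for example, could be an SMT-arm AE through laboratory worsening.

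Protocol 5.3.2 is weak evidence of divergent practice. Holding infusions for bleeding is not a causality attribution, and the adverse-event label is compatible with recording the bleed in both places. It is a classification inconsistency to reconcile.

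The attribution shares have no source in the documents. Protocol 8.3.4 asks investigators to consider whether the subject's clinical state explains the event, which may keep attribution rare.

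Finally, safety comparisons are descriptive, the extra AEs count against the product, and attributed events are visible in the suspected-ADR and causality tables. That softens the AE problem but does not remove it. Those tables identify the attributed events; they do not show how many comparable events occurred under SMT.

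**Conclusion.** The AE half holds on the text alone: for anticipated cirrhosis complications, the by-arm TEAE and serious TEAE tables include attribution-driven events in the Albutein arm only. Its size depends on an attribution rate that the documents do not give; with the assumed 10% to 20% of affected subjects and 20% incidence, it is about 4 to 8 Albutein subjects against none.

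The complication half is conditional. The plan permits, but does not require, attributed events to be left off. If they are, the odds ratio with no true effect is 0.88 to 0.76 at 20% incidence, and further from 1 at higher incidence. If they are recorded in both places, it is 1.00.

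The complication endpoint is exploratory and outside the fixed testing sequence. The primary endpoint and the secondary endpoints (survival, paracentesis count, refractory ascites by ICA criteria) do not use this rule. The point should be corrected because safety is a stated objective and the remedy uses data already collected; it does not threaten the main result.

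**What to change.** 1. **SAP 9.3.8:** state that complications are counted regardless of AE status or causality, as the union of complication-page events and AEs coded to the same terms, in both arms, with an episode found in both records counted once.
2. **SAP 10.1:** add between-arm tables for the listed terms on an equal footing: once included for both arms, drawing on both the AE and complication records, and once excluded for both arms.
3. **Protocol 8.3.10 (with 8.3.3.1) or eCRF guidance:** say that listed events go on the complication page whatever the suspected cause, and are also reported as AEs or SAEs when causality is suspected.
4. **Protocol 5.3.2 and 8.3.10:** reconcile how bleeding is classified. This concerns the label only, not the infusion rule.

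SAP Section 12 indicates that most patients were enrolled under the final amendment, so a new recording rule would not repair data already collected. For those subjects the union in item 1 does the work. The cost is a list of matching coded terms, a few extra tables, and some duplicate entry for suspected-related complications. No visit, dose or treatment rule changes.
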